
8.3 Sample and Recruitment

8.3.1 Eligibility Criteria

8.3.1.1 Inclusion Criteria

- Willing and able to provide informed consent;
- Aged 18 years or older;
- On the waiting list for routine cataract surgery. Cataract surgery as part of a combined procedure with other ocular surgery will not be included;
- No history or presence of significant ocular comorbidities that would be expected to alter the risks of cataract surgery or normal post-operative follow-up schedule. Note that significant ocular comorbidities do not include stable, chronic, or inactive ocular conditions such as amblyopia, drop-controlled stable glaucoma or ocular hypertension, previous squint surgery, inactive macular pathology, previous refractive surgery, or previous vitreoretinal surgery with stable retina.

8.3.1.2 Exclusion Criteria

- Individuals with any condition that could preclude the ability to comply with the study or follow-up procedures;
- Presence of ocular or systemic uncontrolled disease (unless deemed not clinically significant by the Investigator and Sponsor);
- Involved in current research related to this technology or been involved in related research to this technology prior to recruitment;
- Cognitive difficulties, hearing impairment or non-English speakers;
- History of current or severe, unstable or uncontrolled systemic disease (unless deemed not clinically significant by the Investigator and Sponsor).

8.3.1.3 Withdrawing

- Participants will be withdrawn from the study if complications were encountered during their cataract surgery and documented in their medical records. Complications of cataract surgery may include, but are not limited to, capsular tear/rupture, anterior vitrectomy, zonular dehiscence, sulcus intraocular lens implant, dropped lens fragments, other concurrent vitreoretinal procedure;
- Patients who have undergone unplanned clinical review (e.g. eye casualty attendance or any planned appointment as a result of deviation from normal intraoperative course, e.g. suture) or additional ocular procedure prior to the follow-up call will be withdrawn from the study.

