8.2.4 Comparator(s)

Imperial sees all of their post-operative cataract patients at a face-to-face out-patient appointment with an ophthalmologist or specialist nurse. This is conducted between three to four weeks following the procedure. Therefore, patients at Imperial will receive their call from **DORA** within 3 days before their scheduled appointment (day 25-27 post-surgery). This will enable the results of the **DORA** call to be compared with the face-to-face appointment at Imperial to assess whether any complications were correctly identified and if the management plan remains the same.

For patients at both clinical sites, health records will be examined 90 days after the call to determine if the patient presented to an eye clinic with any complications from surgery. This comparison of the follow-up with actual complication rate will enable an assessment of **DORA's** safety (see Table 6).

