8.2.5.2 Secondary Outcomes

There will be several secondary outcome measures to assess the clinical safety, feasibility, usability, and acceptability of the system (see Table 6).

Clinical safety

To examine safety, two outcomes will be captured. Firstly, patients at both sites will have a retrospective case review of both general and ophthalmic electronic health records at 90 days after their initial operation. Complications will be identified from patient's medical records related to any unplanned eye-related clinical episode.

Secondly, all cataract surgery patients at Imperial were historically followed up face-to-face between 3-4 weeks post-surgery in a dedicated post-op clinic. Any complications requiring a change in patient management at slit lamp review or from attending eye casualty services (as the Oxford site does not normally perform face-to-face follow-ups) will be compared with the decisions made by **DORA** and the clinician. If Imperial changes their method of follow-up due to the COVID-19, assessment for complications will be done by checking hospital medical records as is done at the Oxford site.

Feasibility

Feasibility will be assessed by examining the proportion of autonomous calls that were completed without needing any intervention from the supervising clinician. All interruptions or clarifying questions of the supervised call will be logged; the supervising clinician will be asked to log the reason for asking clarifying questions. If clarifying questions were asked because the clinician felt that there was insufficient information for either individual symptoms or to make a management plan, the clinician's management plan before and after clarifying questions will be captured to see if clarifying questions changed the management plan.

Usability

Usability will be assessed using questions presented to patients following calls delivered by online and paper surveys distributed to participants. These questions will be drawn from the System

Usability Scale (SUS) and Telehealth Usability Questionnaire (TUQ; see 13.4 Appendix 4 for a sample survey) [14,15].

Acceptability, satisfaction, and appropriateness

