DORA's acceptability, satisfactoriness, and appropriateness will be assessed during qualitative interviews with a subset of the patients. These semi-structured interviews will provide an opportunity for patients to provide more in-depth feedback about what they liked about **DORA** and any barriers to use that they experienced during the call (see 13.5 Appendix 5 for a sample topic guide). The supervising clinician will also be asked to provide feedback about their level of satisfaction with the system and any safety concerns they might have.

Patients' willingness to recommend **DORA** to others will also be assessed at the end of the call [20]. **DORA** will calculate a net promoter score (NPS) by asking patients "on a scale of 1 to 10, how likely would you be to recommend this automated service to a friend or colleague." **DORA** will follow up by asking patients to "tell me why you gave that score."

Cost-effectiveness

Cost-effectiveness will be examined by collecting and analysing health economic data before and during the study. The costs of implementing **DORA** will be compared with historical data about the costs of the usual standard of care.

| Secondary Outcome | Outcome Measure | | | |
|-----------------------|---|--|--|--|
| Clinical Safety | Complications identified from patients' electronic health records up to 90 days following cataract surgery | | | |
| | Congruence between complications identified and management planned in DORA call and face-to-face follow up (Imperial) Comparison to data from patients attending eye casualty (Oxford) | | | |
| Feasibility | Proportion of autonomous calls that were completed without needing any intervention from the supervising clinician | | | |
| | Clinician-reported reasons for asking clarifying questions | | | |
| Usability | System Usability Scale (SUS) [14,17] | | | |
| | Telehealth Usability Questionnaire (TUQ) [15] | | | |
| | Qualitative feedback from semi-structured interviews | | | |
| Acceptability | Qualitative feedback from semi-structured interviews | | | |
| Satisfaction | Qualitative feedback from semi-structured interviews, Net Promoter Score (NPS) | | | |
| Appropriateness | Qualitative feedback from semi-structured interviews | | | |
| Cost-effectiveness | Comparison of the costs of implementing DORA and the costs of the usual standard of care | | | |
| Identify improvements | Synthesis of all of the outcome measures previously described | | | |

Table 6. Secondary Outcome Measurement

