13.6 Appendix 6. Imperial Historical Recruitment Audit Data

Purpose

To provide real world evidence for assumptions made in modelling of recruitment numbers and study planning.

Audit

We audited all bookings in the cataract one-stop-clinic for the month of October 2020. After discussion with the head of the cataract pathway, it was felt this was the most representative of what the cataract pathway will likely look like in May-July 2021 assuming there is COVID recovery of a similar trajectory to the first wave. It is anticipated there will be 3 consultant-led one-stop clinics running in July to address the backlog. Of note, the general pre-assessment pathways have not been audited.

Key findings

Clinic capacity and utilisation - All October one-stop data

- 33 patients were booked across 4 clinics
- 8.25 patients on average per clinic
- 88% (29/33) attended their one-stop appointments

Conversion rate

- Of all patients booked, 76% proceeded for surgery (25/33)
- Or, of those attending, 86% proceeded to surgery (25/29)

Demographics

- Mean age was 71.5
- This was the first eye for 52% of patients

Inclusion/Exclusion

- 100% (29/29) of those attending were listed for routine cataract surgery
- 10% (3/29) required a translator (Tamil, Punjabi, Arabic)
- 1 patient (3%) had dementia and would not have been able to consent
- Overall, of all attending patients, 76% (29/33) would have been eligible for trial inclusion.

Withdrawal

- No patients in this cohort had unexpected surgical complications
- 1 patient (4%) attended AnE before follow up with a corneal abrasion and would have been withdrawn from **DORA** per our current protocol.

Follow up

- 95% (24/25) of patients attended post-op follow up
- **21%** (7/25) of patients had a documented complication requiring management change at their post-op followup.
 - \circ 6 of these patients were uveitis
 - 4 of which were given maxidex and discharged
 - 1 was given maxidex with phone follow up

- 1 was given maxidex and listed for 2nd eye.
- 1 patient has post-op cystoid macular oedema and maxidex requiring medical retina review.

Pathway

- The mean time between one-stop appointment and surgery was **9.88 days.**
 - The range was from 2 days to 62 days
 - **16 patients** had their operations in under 1 week
- Mean time between surgery and first follow up was 24.33 days.
- A number of patients were followed up under the 21 day point

Comparison with initial estimates

| | Imperial | Imperial |

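### Withdrawing patients who have an unplanned review before the call lowers the complication rate counted from surgery, and leaves the rate counted from the call without its condition stated

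*Protocol*

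**What the plan says.** **Withdrawal.** Protocol 8.3.1.3 covers "Patients who have undergone unplanned clinical review" (eye casualty is an example) or an additional ocular procedure; those affected "prior to the follow-up call will be withdrawn from the study". Under 8.3.3.2, consent is taken at pre-assessment, at listing or in the discharge lounge, so these people are already participants.

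**Outcome counted from surgery.** Section 8.2.5.2 plans a "retrospective case review of both general and ophthalmic electronic health records at 90 days after their initial operation" and counts complications linked to unplanned eye-related episodes. Table 6 has the same start: "Complications identified from patients' electronic health records up to 90 days following cataract surgery".

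**Outcome tied to the call.** Section 8.2.4 says "health records will be examined 90 days after the call to determine if the patient presented to an eye clinic", without giving the start of the look-back. It adds: "This comparison of the follow-up with actual complication rate will enable an assessment of" DORA's safety. Section 8.5.1 counts hospital presentations in the 90 days after the last call, calls this the real complication rate, and derives baseline sensitivity and specificity from it.

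**SAP.** It cross-tabulates DORA's decision against three complication variables from a 3-month audit. It gives no window start, no analysis population and no handling of withdrawn patients.

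**Disclosure.** Section 8.6 does not mention this selection. Section 8.7 counts only intraoperative complications (about 2.5%) as exclusions, and concludes that positive results would show potential for nearly all follow-up assessments.

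**Audit.** Appendix 6 reports one Imperial patient who "attended AnE before follow up with a corneal abrasion and would have been withdrawn from" the study.

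**The concern.** The event that triggers withdrawal is the kind of event that the post-surgery outcome counts. A patient whose complication shows itself early and leads to an eye casualty visit drops out of both numerator and denominator. The published figure would then describe patients who got as far as the call without needing an unplanned review. A reader of Table 6 would take it as the rate after uncomplicated cataract surgery.

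Two uses are at stake. The rate is presented as a safety benchmark for the call. The accuracy figures are meant to inform later evaluations, whose planners need to know which patients the figures describe.

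**Working it through.** **Inputs**
- Pre-call withdrawal share, w: 1 of 25 operated patients at Imperial (Appendix 6).
- Later presentation rate, c: 1 emergency attendance at 10 weeks at Oxford (Appendix 7). Of 30 operated patients, 2 had surgical complications, so the base is 30 − 2 = 28.
- Call time: "day 25-27 post-surgery", Imperial only (8.2.4). No call day is given for Oxford.
- Planned size: 591, after a 15% dropout allowance (Table 7).

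**Step 1. The plan's own figure.** 1/25 = 4.0%, as printed in Appendix 6. The Clopper-Pearson 95% CI is 0.1% to 20.4%.

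**Step 2. Patients affected.** 591 is already net of dropout, so the recruited base is 591/0.85 = about 695. At 4%, 0.04 × 695 = about 28 patients. The confidence limits for w give about 1 to 142.

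**Step 3. Share of the window (Imperial).** 25/90 = 27.8% and 27/90 = 30.0%. Over that part of a post-surgery window, analysed patients can contribute no known unplanned review. The remaining 63 to 65 days are fully observed. This is a share of time, not of events.

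**Step 4. Effect on the post-surgery rate.** Treat each pre-call unplanned review as an event.
- Rate over all consented patients with uncomplicated surgery: w + (1 − w)c
- Rate the study observes: c
- Shortfall: w(1 − c), which is positive whenever w > 0 and c < 1

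With c = 1/28 = 3.6%, assumed for both sites:

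| w | Rate over all, w + (1 − w)c | Observed | Observed as share of all |
|---|---|---|---|
| 1% | 0.01 + 0.99 × 0.0357 = 4.5% | 3.6% | 79% |
| 4% | 0.04 + 0.96 × 0.0357 = 7.4% | 3.6% | 48% |
| 10% | 0.10 + 0.90 × 0.0357 = 13.2% | 3.6% | 27% |

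**Step 5. The post-call window.** At Imperial, 90 days after a call on day 25 to 27 runs to day 115 to 117. Pre-call episodes fall outside it by definition, so the withdrawal rule causes no shortfall in that quantity.

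**Step 6. Imperial's planned visit.** Complications that change management at the slit lamp also count towards clinical safety (8.2.5.2). Appendix 6 lists 7 of 25. It prints 21%, but 7/25 = 28.0%; 21% matches 7/33, the number booked.
- If the abrasion patient is among the seven: 6/24 = 25.0% after withdrawal, against 7/25 = 28.0%.
- If not, and the abrasion is counted as an event: 7/24 = 29.2%, against 8/25 = 32.0%.

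Either way the shift is about 3 percentage points.

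**The case against.** The best defence is that an eligibility rule and an outcome window can coexist. No objective in 7.5 is to estimate how often complications follow cataract surgery. The record review is there to check the call's decision, and 8.5.1 separates complications that the call missed from those that arose later. A patient reviewed before the call has no DORA decision to check. Safety is judged mainly by agreement and the two-by-two tables, not by a low crude rate.

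Much of this stands, and it rules out several stronger readings that a reader might infer:
- *The complication rate is understated on every definition.* It is not. The 8.5.1 definition starts at the last call.
- *Sensitivity and specificity are biased.* They are not. The rule fixes the population to which they apply.
- *Imperial's rate would fall from 4% to 0%.* This ignores the seven management changes at the planned visit, and Appendix 6 describes no 90-day record review.
- *No unplanned episode before the call can remain.* The rule removes known clinical reviews. A telephone contact that needed no review, like the one in Appendix 7, or a visit unknown at the time of the call, could stay in.

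It is also fair that the protocol does not say that records of withdrawn patients go unreviewed. It does not say that they are reviewed either, and the SAP is silent.

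The defence does not dispose of the definition in 8.2.5.2 and Table 6, which starts at surgery. Nor does it explain why a rate restricted to patients who reach the call carries an unqualified label.

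**Conclusion.** The point holds for the outcome as defined in 8.2.5.2 and Table 6: the rate from surgery is biased downward if any consented patient is withdrawn for a known unplanned review that would have counted. For the 8.5.1 outcome the fault is one of labelling. The condition on reaching the call is not stated there, in the SAP, or in 8.6 and 8.7.

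The direction is clear, but the size is not. Observing 3.6% where the full rate is 7.4% illustrates what one patient in 25 and one in 28 would imply; with 1% withdrawn, the full rate is 4.5%. These figures assume that:
- withdrawal means removal from the record review;
- every pre-call unplanned review counts as a complication (if only some do, the gap is smaller);
- the Oxford attendance rate applies at both sites, although Appendix 7 does not say that all 28 patients were followed for 90 days.

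The 28% to 30% share of the window is for Imperial only, and the slit-lamp measure there moves by only about 3 points.

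**What to change.** 1. Use one start and one end for the complication window in 8.2.4, 8.2.5.2, Table 6, 8.5.1 and the SAP. If it runs from the call, give the post-surgery rate in item 3 as a supplementary result with its own stated window.
2. In 8.3.1.3, keep patients with an unplanned review before the call in the planned 90-day record review, where consent allows. Who is called does not change.
3. Report the post-surgery rate over all consented patients with uncomplicated surgery, with those who presented before the call as a separate row, by site.
4. State in the SAP and in 8.6 and 8.7 that DORA's sensitivity and specificity are conditional on no unplanned review before the call.

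The cost is some extra record reviews (about 28 if the audit's 4% holds), one table row per site and a few sentences. The reported complication rate will be higher. Whether the consent wording permits record review after this kind of withdrawal was not checked here and needs confirming first.

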8.3.2 Sampling

8.3.2.1 Sample Size

An audit of historical data was conducted for both Imperial and Oxford sites to provide evidence for an estimate of the study's sample size (see Appendices 7 and 8, respectively). All types of pre-assessment appointments throughout October 2020 were audited. October 2020 was used to project capacity in May-July 2021 on the assumption that recovery from this wave of the Covid-19 pandemic would follow a similar trajectory to recovery from the first wave. At Imperial, three consultant-led one-stop clinics are expected to be in place in July to mitigate surgery backlog. Sample size calculations were based on estimates deriving from this audit. As outlined in Table 7, Imperial currently sees about 7 patients per week in their one-stop clinic and pre-assesses about another 64 per week, almost 90% of whom are listed for surgery. If 80% of the total patients seen are estimated to be eligible for the trial, approximately 230 patients could be recruited from this clinic over the course of the study period. At Oxford, about 60 new patients are seen for pre-assessment per week, with approximately another 20 phone assessments for second eye are also done, with 90% being listed for surgery. With an estimated 70% of patients consenting to participate, and an attrition rate of 15%, 591 patients are expected to be recruited over the course of 26 weeks. An *a priori* power calculation was conducted to determine the minimum sample size necessary to achieve a power greater than 0.8 for a 0.05 level of significance [21]. On the basis of a total population of 1014, a 95% confidence level, and a 3% margin of error, a sample size of 520 is required for statistical significance.

| is set at 2 days due to | Imperial | Imperial | | Oxford | Oxford |
|---|--|---|--|----------------|--------------------------------------|
| | One-stop (Projected 3 clinics per week from 1/2021) | Pre-assessment (excluding one-stop) | | Pre-assessment | Phone pre-assessment (2nd eye) |
| Current Numbers Asso | essed | | | | |
| Mean Patients assessed per clinic | 10 | 8 | | 12 | 4 |
| Clinics per week | 3 | 8 | | 5 | 5 |
| Mean Patients Assessed per week | 30 | 64 | | 60 | 20 |
| Eligibility Assumption: | S | | | | • |
| % proceeding to surgery | 80% | 90% | | 90% | 90% |
| % routine cases | 80% | 80% | | 80% | 80% |
| % eligible for trial | 80% | 80% | | 90% | 90% |
| % ineligible due to complicated surgery | 5% | 5% | | 5% | 5% |
| Screening | | | | | |
| Compound daily eligibility rate | 49% | 55% | | 62% | 62% |

Table 7. Indicative recruitment targets with assumptions of dropout at each stage. Screening capacity is set at 2 days due to staffing constraints.

| Number of days screening | 2 | 2 | | 2 | 2 |
|--|-----|-----|-----|-----|-----|
| Patients screened per week | 10 | 9 | | 15 | 5 |
| Estimated recruitmen | t | | | | |
| % consenting to trial | 70% | 70% | | 70% | 70% |
| Estimated average recruited per week | 7 | 6 | | 10 | 3 |
| Duration of trial (weeks) | 26 | 26 | | 26 | 26 |
| Estimated % of patients dropping out | 15% | 15% | | 15% | 15% |
| Estimated recruitment over trial | 150 | 135 | | 229 | 76 |
| Site Total | 286 | | 305 | | |
| Total | 591 | | | | |

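### The 591 patients called recruited, and given as the planned sample size, are what is left of about 695 consented after 15% dropout; and not all of the inputs come from the audit named as their source

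*Protocol*

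**What the plan says.** **Target.** Section 8.3.2.1 mentions 70% consent and 15% attrition and then says that "591 patients are expected to be recruited over the course of 26 weeks". Table 7 labels the same total as estimated recruitment over the trial, and the Study Summary (section 5) calls it the planned sample size. Section 8.3.3.1 continues screening until a target enrolment is reached, but gives no number and does not say what is counted. The requirement is set at 520, "On the basis of a total population of 1014" with 95% confidence and a 3% margin of error. Section 9.8 describes the estimated sample as close to the minimum. The SAP does not mention sample size.

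**Source.** Section 8.3.2.1 says that "All types of pre-assessment appointments throughout October 2020 were audited" and that "Sample size calculations were based on estimates deriving from this audit". It says of Oxford that "about 60 new patients are seen for pre-assessment per week", with about another 20 phone assessments. It says of the Imperial one-stop clinic that "approximately 230 patients could be recruited from this clinic over the course of the study period". Appendix 6 states that Imperial's general pre-assessment pathways were not audited. Appendix 7 heads the 60 and 20 a week as study projections, beside an October 2020 column showing 39.5.

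**The concern.** The word recruited normally means consented and enrolled. A site that reads the Study Summary could treat 591 consents as the finish line, although Table 7 counts only patients who remain after dropout. Taken as evaluable patients, 591 exceeds 520 by 71. Taken as consents, it falls short of 520 once the protocol's own dropout rate is applied. The two readings lie on opposite sides of the protocol's own threshold, and no sentence chooses between them.

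The statement of source matters less for conduct, but it tells the reader that the volumes in Table 7 are observed. For part of the table the appendices say otherwise.

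**Working it through.** **1. Reproduce 591.** Inputs are from Table 7. For each column: mean per clinic × 2 screening days × compound eligibility × 0.70 consent × 26 weeks × 0.85 retained. Compound eligibility is the share proceeding to surgery × routine × eligible × 0.95.

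| Column | Per clinic × 2 | Compound | Screened/week | Consented, 26 weeks | After 15% dropout |
|---|---|---|---|---|---|
| Imperial one-stop | 20 | 0.4864 | 9.73 | 177.0 | 150.5 |
| Imperial pre-assessment | 16 | 0.5472 | 8.76 | 159.3 | 135.4 |
| Oxford pre-assessment | 24 | 0.6156 | 14.77 | 268.9 | 228.6 |
| Oxford phone | 8 | 0.6156 | 4.92 | 89.6 | 76.2 |
| Total | | | 38.18 | 694.9 | 590.7 |

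The printed 591 is the last column, so it is net of dropout. Table 7 uses the word recruited in two senses: its weekly row is before dropout and its trial total is after dropout.

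**2. Reproduce 520.** With p = 0.5 (not stated, but it returns the printed figure), n0 = 1.96² × 0.25 / 0.03² = 1067.1. With the finite-population correction, 1067.1 / (1 + 1066.1/1014) = 520.

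**3. If 591 were the number consented.** 591 × 0.85 = 502, which is 18 below 520. The margin of error at N = 1014 is 1.96 × √[(0.25/n) × (1014 − n)/1013]. This gives 3.00% for n = 520 and 3.11% for n = 502.

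**4. Consents needed.** 591/0.85 = 695.3, so 696. The 695 in step 1 is the unrounded Table 7 total before dropout. 520/0.85 = 611.8, so 612. Against stopping at 591 consented, these are 696 − 591 = 105 and 612 − 591 = 21 more.

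**5. Complicated surgery.** Table 7 removes 5% for complicated surgery before consent. Section 8.3.3.2 allows consent at pre-assessment, and section 8.3.1.3 withdraws patients whose surgery was complicated. If all consent came before surgery and none of these withdrawals were inside the 15%, the needs would be 591/(0.85 × 0.95) = 732 and 520/(0.85 × 0.95) = 644. These are upper values, because consent in the discharge lounge after surgery is also allowed.

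**6. Source, side by side.**
- Audit scope: section 8.3.2.1 claims all pre-assessment types. Appendix 6 excludes Imperial general pre-assessment, which supplies 135 of the 591.
- Oxford volume: the text and Table 7 give 60 a week as current. The October 2020 figures in Appendix 7 are 160/21 = 7.6 per clinic, or 7.6 × 5 = 38 a week (39.5 as printed). The 12 per clinic is a projection.
- Oxford phone: 20 a week in Table 7, against 1 of 160 bookings in the audit. This stream supplies 76 of the 591.
- Imperial one-stop: the text's 230 matches the projection of 228 in Appendix 6, which has 90% consent and no dropout: 20 × 0.4864 × 0.90 × 26 = 227.6. Table 7 gives 150.

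**The case against.** The strongest defence is disclosure. The sentence giving 591 names the 15% attrition, and Table 7 prints the dropout row just above the result, so a careful reader can recover about 695. Table 7 is titled as indicative, has a block of assumptions, and heads the one-stop column as projected. Appendices 6 and 7 set audit and projection side by side. No sentence tells sites to stop at 591 consents, and section 8.1.1 also ends recruitment by time, about 6 weeks before calls end. The 520 is a margin of error for a proportion, whereas section 8.5.1 makes kappa the primary analysis, so falling below 520 has no shown effect on that analysis.

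Much of this stands. The gross number can be derived, the appendices do allow a comparison of audit with projection, and the harm depends on a reading that the text permits but does not require. The defence does not remove the ambiguity: 695 appears nowhere, and nothing says whether the target counts consented or evaluable patients. Nor does the word indicative correct a statement that everything was audited when Appendix 6 says it was not.

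A reader might also take "Imperial currently sees about 7 patients per week in their one-stop clinic" to contradict the 30 a week in Table 7. That is mostly current against projected, since the text expects three clinics by July and the column header says so. Only the table's row label, which calls the numbers current, is loose. The 230 is a leftover that does not feed 591.

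**Conclusion.** The main point holds: 591 is an evaluable count labelled as recruitment and as the planned sample size, with no defined enrolment target. Stopping at 591 consented would leave about 502, which is 18 under the protocol's own requirement, at a cost in precision of about 0.1 percentage point. This assumes that the 15% dropout occurs as planned and that those patients give no primary-outcome data.

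The secondary point also holds: the stated audit scope is contradicted by Appendix 6, and Oxford's 60 plus 20 a week are projections presented as current.

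Two stronger readings are not supported. One is that the sample-size arithmetic is wrong; both 591 and 520 reproduce. The other is that audit values show that recruitment will fail. Any such forecast would rest on the 70% consent rate, which has no audit source (the appendices use 90%), and section 8.1.1 allows calls over six to twelve months so that targets can be met. The forecast is not fully supported by its stated source; it is not shown to be wrong. The correction should be made, but it does not touch the design or the analysis.

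**What to change.** 1. In section 8.3.2.1, the Study Summary and section 8.3.3.1, state the enrolment target as consented patients with the evaluable number beside it: 696 consented for 591 evaluable, or 612 for 520.
2. Say whether the 15% includes withdrawals for complicated surgery after consent at pre-assessment. If none are included and all consent precedes surgery, the figures rise to at most about 732 and 644.
3. Correct the sentences on audit scope, on the source of the calculation, on Oxford's 60 plus 20 a week, and on the 230 from the one-stop clinic.
4. Mark each Table 7 input as audited, projected or unaudited. Justify or drop Oxford's 12 per clinic and the phone stream.
5. Clerical: relabel the rows headed as current numbers, and correct "see Appendices 7 and 8, respectively", since the audits are Appendices 6 and 7.

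Cost: some sentences, one relabelled table and one definition. Keeping 591 evaluable needs about 105 more consents than stopping at 591 consented; 520 evaluable needs 21 more. On the upper assumption in item 2 these become 732 − 591 = 141 and 644 − 591 = 53. Alternatively, the sponsor can keep 591 consented, restate the expected evaluable number as about 502, and accept a margin of about 3.1%. Dropping the phone stream would take its 76 off the 26-week total.
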